8 STUDY PLAN

This is a phase II, randomized, double masked, multicentre, national study.

This study will be carried out with 60 eyes with diagnosis of bacterial conjunctivitis, by treatment group, of patients of the ophthalmological consultation.

Patients diagnosed with bacterial conjunctivitis (signs and / or symptoms and / or culture) recruited will be treated for 7 days with any of the three posologies of PRO157, Moxifloxacin, or Gatifloxacin. The randomization of any of the medications will be coordinated by a member of the research team previously designated who will not be masked and will be responsible for indicating to the patients how to apply the drops, emphasizing the patients of by no means mentioning the evaluating physician with the frequency who applies the study medication.

No patient may use the aforementioned treatment more than the prescribed time. For purposes of the protocol, the infected eye (s) will be taken into account at baseline but the study medication and procedures will be applied and will always be done in both eyes to protect the healthy eye and the possibility of infection if Do not be infected from the beginning.

The study is divided into the following periods:

There will be a total of 3 visits which are divided into 1 baseline visit (day 1) 1 treatment visits (day 3), 1 final visit (day 8). A telephone call will finally be made to evaluate adverse events after 15 days of the last application of medication (day 23)

At each visit from the baseline a clinical photograph of the eyes will be made, each of them must be identified by patient and visit number and delivered once the 30 patients are completed on a CD or USB.

1. Period of treatment of 7 days (from day 1 to 7) where any of the following posologies are applied according to randomization:

PRO157 1 drop 2 times a day in both eyes.
PRO157 1 drop 3 times a day in both eyes.
PRO157 1 drop 4 times a day in both eyes.
Moxifloxacin 1 drop 3 times a day in both eyes
Gatifloxacin1 drop 3 times a day in both eyes

The study medications will be delivered by a coordinator (not blinded) or a person previously designated by the principal investigator, who will indicate how to apply the study medication according to the randomization and will place special emphasis on not mentioning the principal investigator or designee. perform the evaluations as the drop or any characteristic of the jars is applied.

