An artificial lagrima without conservative Lagricel Ofteno® will also be applied one drop 4 times a day to all patients who enter the study during the 7 days of treatment with the study medication.

The valuation days indicated in Figure 1 of the Study Plan must be carefully observed. A variation of ± 1 days can be accepted in relation to the inclusion visit (from day 1 to 8). In the case of the inclusion of subjects from 0 years to less 18 years minus 1 day, they will be included progressively as follow:

- Age group of 12 to 18 years.
- Age group from 2 to 12 years old.
- Age group from 0 to 12 years old.

This with the intention of integrating patients once the dosage parameters have been established as safe and recommended for the younger age groups.

The indications of the inclusion periods will be made as the results are gathered in the groups of minors.

Blinding

The double-blind study is a procedure in which the patient and the attending physician do not know which of the intervention groups was assigned by the study patient. The blinding codes are protected by a person outside the study.

Figure 1 - Plan of the Study

[figure not shown]

Table 2: Timeline

Procedimiento	Visita Basal				
		Visita 1	Visita Final	Seguimiento Telefónico EA	Visita no programada / Descontinuación
	Día 1	Día 3	Día 8	Día 23	
Criterios de Elegibilidad	X				
Firma de consentimiento informado	X				
Datos demográficos	X				
Prueba de embarazo en orina (si aplica)	X		X		
Historia Clínica General y Oftalmológica	X				
Padecimiento actual					X
Toma de muestra para cultivo	X		X		
Fotografía clínica de los ojos	X	X	X		
Asignación de número al paciente	X				
Entrega de medicamento	X				
Inicio de aplicación de medicamento	X				
Aplicación de medicamento	X	X	X		
Devolución de medicamento por parte del paciente			X		
Sintomatología Ocular (A,B,C,D)	X	X	X		X
Agudeza y/o Capacidad Visual	X	X	X		X
Biomicroscopia anterior (F,G,H,I,J,K)	X	X	X		X
Tinciones de fluoresceína/verde de lisamina	X	X	X		
Revisión del segmento posterior (L,M,N,O)	X	X	X		X
Evaluación de eventos adversos	X	X	X	X	X
Evaluación de medicamentos concomitantes	X	X	X		X

A) Burning B) Lachrymation C) Foreign body sensation D) Pruritus E) Photophobia DF) Conjunctival hyperemia G) Chemosis H) Secretion I) Eyelid edema J) Membranes and / or pseudo-membranes K) Epitheliopathy L) Vitreous M) Retina N) macula O) optic nerve.

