16 TREATMENT OF STUDY SUBJECTS

16.1 Managed treatments

Lagricel Ofteno® Apply one drop 4 times a day for 7 days + any of the following according to the randomization in both eyes.

Apply one drop of PRO157, 2 TIMES a day, from day 1 to day 7
Apply one drop of PRO157, 3 TIMES a day, from day 1 to day 7
Apply one drop of PRO157, 4 TIMES a day, from day 1 to day 7
Apply a drop of Moxifloxacin, 3 TIMES a day, from day 1 to day 7
Apply a drop of Gatifloxacin, 3 TIMES a day, from day 1 to day 7

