16.5 Compliance with treatment

- With the accounting of the study medication returned.

- Patients will have a "diary of the subject" where they will have to write down the time of application of the drop and any incident or setback at the time of the application of the drop, for example, forgetfulness in the application of the drop, application of extra drops, etc.

- The adherence to treatment must be greater than 80%

After the discontinuation of the study treatment, the subject will return with the previously used treatment.

17. Methods and times of measurements.Scales to fill out by the researcher:

A meeting of researchers will be organized for all those involved in carrying out the study before starting it, and their participation will be mandatory. The objective of these sessions is to train them on the assessment of the efficacy and safety criteria and to ensure reliability among the qualifiers. In addition, detailed qualification rules will be provided to the qualifiers

The scales should always be evaluated by the same evaluating physician, either the principal investigator or an ophthalmologist previously designated in the Delegation of Responsibility format throughout the study, at the beginning of each visit. A guide will be made available for the interview to be carried out in each of the visits.

Self-qualification questionnaires to be completed by the patient:

Initials of the subject	
-------------------------	--

Mark with an X in any of the following options with which you have identified more in the course of the clinical study.

DEGREE OF SATISFACTION OF THE SUBJECT	ANSWER
Very bad: Intense and unbearable nuisances.	
Mal: Moderate intensity, intermittent, not tolerable.	
Regular: Discomfort of moderate intensity, intermittent and tolerable.	
Good: Mild and occasional nuisances.	
Very good: No discomfort (absent).	

The researcher will apply to the subject a questionnaire that he / she will have to answer at the end of the study where the satisfaction is evaluated upon finishing his / her participation in the study.

Visual acuity

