18.2 Times of Measurements

Clinical examination

Basal visit (Day 1)

The principal investigator or the head of the research team of the site duly specified must obtain the letter of informed consent of each of the subjects, before carrying out any procedure of the study.

When the informed consent is obtained and all the inclusion criteria and none of exclusion are met, a unique identification number of the subject will be assigned, this will be used throughout the study for its identification.

Female subjects who are of reproductive age will be tested for pregnancy in urine.

The following evaluations will be made:

Signature of informed consent

Review of inclusion criteria and exclusion criteria,

Demographics,

Urine pregnancy test (if applicable),

General and ophthalmological clinical history,

Clinical Photography,

Sampling of conjunctival sac fundus for culture,

Assigning number to the subject,

Delivery of medication,

Ocular symptoms: burning, tearing, foreign body sensation, pruritus, photophobia

Visual acuity and / or visual ability,

Anterior biomicroscopy: Conjunctival hyperemia, chemosis, secretion, palpebral edema, membranes and / or pseudomembranes, scales, epitheliopathy,

Fluorescein staining,

Green stain of lysine,
Posterior segment revision: Retina, Macula, Vitreous and Optic nerve.
Evaluation of adverse events.

This day the patient will be included, if clinically it suggests a bacterial conjunctivitis, it will be randomized and at that same moment a clinical photograph of his eyes will be made and a sample will be taken for culture of both eyes, immediately he will go with the person previously designated to randomize him, this person will not be masked and will give specific instructions to the patient on how to apply the study medication and will remember the importance of the patient not mentioning the study's evaluating physician how many times the treatment is applied, then he will start with the study medication regardless of the crop results.

Treatment visits:**Visit 1 (Day 3)**

Between the days of study there may be a window of \pm 1 day. If for any reason an assessment is made on any day not planned in the study, this information should be recorded in the unscheduled visit format found within the FRC.

At each follow-up visit, an ophthalmological examination will be performed in order to evaluate the following parameters.

1. Acuity and / or Visual Ability
2. Clinical Photography,

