3. Evaluation of specific symptoms and signs: burning, tearing, foreign body sensation, pruritus, photophobia,
4. Anterior biomicroscopy: conjunctival hyperemia, chemosis, secretion, palpebral edema, membranes and / or pseudomembranes, scales, epitheliopathy.
5. Posterior biomicroscopy (retina, vitreous, macula and optic nerve).
6. Fluorescein staining
7. Green lysine stain
8. Evaluation of adverse events.
9. Evaluation of concomitant medications.

Final Visit (Day 8)

In this the following parameters will be evaluated:

1. Urine pregnancy test (if applicable)
2. Return of medication by the subject
3. Acuity and / or Visual capacity
4. Clinical photography,
5. Ocular symptoms: burning, tearing, foreign body sensation, pruritus, photophobia.
6. Conjunctival sac fundus sampling for culture
7. Anterior biomicroscopy: conjunctival hyperemia, chemosis, secretion, palpebral edema, membranes and / or pseudomembranes, scales, epitheliopathy.
8. Posterior biomicroscopy (retina, vitreous, macula and optic nerve).
9. Fluorescein staining
10. Green lysine stain.
11. Evaluation of adverse events
12. Evaluation of concomitant medications

Follow-up of Adverse Events (EA) (Day 23)

1. A telephone call will be made by the investigating doctor or responsible previously designated for the evaluation of adverse events.

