$Z_{1-\alpha/2} = Z_{0.975}$ de la distribución normal estandarizada que deja un area de 0.975 a la izquierda. Implica una confiabilidad del 95% 1.960

β = Probabilidad de error tipo 2 0.200

$1-\beta$ = Percentil unilateral para la beta asignada 0.800

$Z_{1-\beta} = Z_{0.80}$ de la distribución normal estandarizada que deja un area de 0.80 a la izquierda. Implica un poder del 80% 0.842

m' = Tamaño de muestra

$$m' = \frac{(z_{1-\alpha/2} \sqrt{(r + 1) * P * Q} + z_{1-\beta} \sqrt{r * P1 * Q1 + P2 * Q2})^2}{r * (P2 - P1)^2}$$

$$m' = \frac{(1.960 \sqrt{(1.00+1) 0.79 * 0.21} + 0.842 \sqrt{1.00 * 0.92 * 0.08 + 0.66 * 0.34})^2}{1.00 (0.66 - 0.92)^2}$$

$$m' = 36.373$$

m = Tamaño de muestra corregido

$$m = 0.25 m' * \left[1 + \sqrt{1 + \frac{2(r + 1)}{m' * r * |P2 - P1|}} \right]^2$$

$$m = 44 \quad \begin{array}{l} \text{Tamaño de muestra para el grupo de referencia (Controles): } m_1 = r * m \\ \text{Tamaño de muestra para el grupo de estudio (Casos): } m_2 = m \end{array} \quad \begin{array}{l} 44 \\ 44 \end{array}$$

Analyzed data set

The data will be analyzed in two groups, one will be made up of the population evaluable by Intention to Treat (ITT) in which each of the variables is described, the ITT population will be constituted by all the recruited subjects who have received at least one dose of study treatment.

Others will be the evaluable population Per Protocol (PP) which is the subset of ITT composed of all subjects without any major deviation from the protocol, in which the bivariate analysis will be performed.

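### The ±1 day window and a day-8 drug mark in Table 2 each allow the end culture to be taken on a dosing day, and no rule covers such swabs

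*Combined protocol and SAP*

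**What the plan says.** - **Dosing.** Section 8 sets a "Period of treatment of 7 days (from day 1 to 7"). Section 16.1 repeats those days for every arm, for example "Apply one drop of PRO157, 4 TIMES a day, from day 1 to day 7". PRO-157 is given two, three or four times daily; moxifloxacin and gatifloxacin are each given three times daily.
- **Final visit.** This is day 8. Section 18.2 lists "Conjunctival sac fundus sampling for culture" and "Return of medication by the subject" among its procedures.
- **Visit window.** Section 8: "A variation of ± 1 days can be accepted in relation to the inclusion visit (from day 1 to 8"). Section 18.2, under Visit 1, adds "Between the days of study there may be a window of" one day either way.
- **Table 2 (Section 8).** The drug-application row is marked at day 1, day 3 and day 8.
- **Adherence.** Sections 9 and 16.5: "The adherence to treatment must be greater than 80" per cent.
- **Analysis sets (Section 23).** ITT requires one dose. The per-protocol set consists of "all subjects without any major deviation from the protocol, in which the bivariate analysis will be performed".
- **Role of the culture (Section 7.1).** The main efficacy criterion compares baseline and final cultures, and microbiological remission alone is enough to count treatment as effective.

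**The concern.** An end-of-treatment culture should show what survives the course. A swab taken hours after an antibiotic drop may fail to grow bacteria that are still present. If that happens, part of the apparent eradication reflects recent dosing.

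The PRO-157 arms differ only in dosing frequency. On a dosing day, frequency also affects how long before the swab the last drop was given, so an artefact of sampling time could be mixed with the schedule effect the trial sets out to compare. Separately, returning the drug on day 7 cuts the 7-day course short.

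**Working it through.** The plan gives no calculation on this point, and its sample-size figures do not enter. The check uses day arithmetic, drop counts, and clock times that have to be assumed.

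**1. Can the swab fall on a dosing day?**
- By the window: 8 − 1 = day 7, the last day on which drops are due in all five arms. A visit inside the window is not in itself a deviation.
- By Table 2: if the day-8 mark is followed, day 8 is itself a dosing day. This conflicts with Sections 8 and 16.1.

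**2. Would the adherence rule catch a day-7 return?** Let k be drops per day, a the drops on day 1 and b the drops on day 7, with days 2 to 6 complete. Adherence = (a + 5k + b) / 7k. The plan states no denominator; the full course of 7k drops per eye is assumed.

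| Drops taken | 2× (of 14) | 3× (of 21) | 4× (of 28) |
|---|---|---|---|
| Full day 1, none on day 7 | 12 = 85.7% | 18 = 85.7% | 24 = 85.7% |
| Two drops in all over days 1 and 7 | 12 = 85.7% | 17 = 81.0% | 22 = 78.6% |
| One drop on day 1, none on day 7 | 11 = 78.6% | 16 = 76.2% | 21 = 75.0% |

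A patient with six full days passes in every arm. After a partial day 1 the rule flags some returns, and in the middle row only those in the four-times-daily arm. A partial day 1 is plausible, because Section 18.2 starts the drug only after the baseline examination, culture and randomization. No text says what failing the rule means for the culture.

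**3. Does the time since the last drop differ by schedule on day 7?** Assumptions: drops evenly spaced from 8:00 to 20:00 or from 8:00 to 22:00, all taken on time; visits spread evenly from 9:00 to 17:00.

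| Time since last drop, day 7 | 2× | 3× | 4× |
|---|---|---|---|
| Mean, last drop at 20:00 | 5.0 h | 2.75 h | 2.0 h |
| Mean, last drop at 22:00 | 5.0 h | 3.25 h | 2.5 h |
| Visit at 17:00, last drop at 20:00 | 9 h | 3 h | 1 h |
| Visit at 17:00, last drop at 22:00 | 9 h | 2 h | 4.3 h |

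Example for 3× with drops at 8:00, 14:00 and 20:00: from 9:00 to 14:00 the gap averages 3.5 h over 5 h, and from 14:00 to 17:00 it averages 1.5 h over 3 h. (17.5 + 4.5) / 8 = 2.75 h.

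At 9:00 or 11:00 the schedules do not differ, because each patient's last drop was at 8:00. In the last row the order of 3× and 4× reverses.

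**4. What would day 8 give?** If dosing ends on day 7 and nothing is given on day 8, a 9:00 swab comes 13 h after a 20:00 drop or 11 h after a 22:00 drop, equal in all arms under the same clock assumptions. This holds only if the Table 2 mark is removed or not followed.

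**The case against.** The strongest case against has five parts.

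- **The window's reach is not beyond doubt.** The Section 18.2 sentence sits under Visit 1, the final-visit list states no window, and Section 8 tells sites to observe the days in Figure 1, which is not shown in the text available. Even so, the Section 8 sentence names a range ending on day 8, so the final visit is covered on its ordinary reading.
- **A reader might infer that the plan keeps dosing-day swabs in the per-protocol set.** The documents do not support that. Major deviation is undefined, and a course cut short could be classed as one even when the visit is in window. The plan is silent.
- **A reader might infer that the adherence rule never catches a day-7 return.** After a partial day 1 it can, as the table shows. What is missing is a stated consequence for the culture.
- **The Table 2 mark might be dismissed as a slip.** Section 8 forbids use beyond the prescribed time, which favours that view, but no text settles it. If the mark is intended, the nominal schedule itself produces dosing-day swabs, and changing the window alone would not cure the problem.
- **The bias is conjectural and limited.** The documents give no share of day-7 visits and no effect of recent dosing on culture growth. The window applies to every arm. PRO-157 three times daily and both comparators share one frequency, so schedule creates no imbalance there. Clinical remission alone also counts as success, so the culture decides only some patients.

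The last part stands and limits the point to a minor one. It does not remove the gap in the rules.

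**Conclusion.** The concern holds as a minor point that is cheap to correct. A stated rule permits the end culture and drug return on day 7, and a table entry conflicts with the text on whether day 8 is a dosing day. Either route can put the swab on a dosing day. The window can also reduce the course to six full days, assuming a complete day 1. No minimum interval before the swab is given in the text, and the handling of such cultures in the per-protocol set is undefined.

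The adherence counts rest on a denominator of seven full days; the hours rest on assumed clock times. A reader might go on to infer that the window favours more frequent dosing. The documents do not support that: they fix neither size nor direction, and under the assumed times the ordering changes with the hour of the visit. Any effect is confined to swabs taken on a dosing day where the culture decides success, and dosing frequency can contribute to it only between arms with different frequencies.

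**What to change.** - In Sections 8 and 18.2 write: final visit, end culture and drug return on day 8, window 0/+1 day, no study drug after day 7.
- Remove the day-8 drug-application mark in Table 2 so that dosing ends on day 7 throughout.
- Record any culture taken on a dosing day as a deviation.
- Repeat the culture comparison without those eyes, identified from visit dates.

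The cost is one line in each of two sections, one table mark, and one repeat analysis from dates already collected. The downside is slightly less visit flexibility: a patient who can attend only on day 7 becomes a recorded deviation. Visit dates are enough for this. If time since the last drop is also wanted, the unmasked coordinator should take it from the diary and keep it from the evaluator, because diary times reveal the dosing frequency.

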7 STUDY DESIGN

7.1 Point or limit points

Criteria for the evaluation.

Efficacy measurements:

Main efficacy criterion

Efficacy will be determined by taking cultures of the lower conjunctival cul-de-sac background quantifying (colony-forming units) and identifying genus and basal and final microbial species.

It will be determined as effective if there is a reduction in the number or species of bacterial flora comparing the basal culture against the end between the five different groups of patients and / or if there is a reduction or absence of the following specific signs and symptoms: burning, tearing, Foreign body sensation, pruritus, photophobia, conjunctival hyperemia, chemosis, palpebral edema and secretion, membranes and / or pseudomembranes when comparing the study medication versus Moxifloxacin and versus Gatifloxacin from baseline to final visit.

Efficiency parameters

- The effectiveness of the drug will be evaluated by means of:

1. Clinical referral

2. Microbiological remission

Clinical remission will be evaluated by means of the signs and symptoms that the patient presents at the beginning and at the end of the study.

Variable	Operationalization	Measurement scale	Value
Secretion	Dependent Qualitative ordinal	Absent Present	Must be recorded as absent in 95% of the subjects evaluated
Conjunctival hyperemia	Dependent Qualitative ordinal	Absent Mild Moderate Severe	You must comply with the following: • Absent \geq 95.0% • Mild \leq 5.0% • Moderate \leq 2.5% Severe \leq 1.0%
Chemosis	Dependent Qualitative ordinal	Absent Present	Must be recorded as absent in 95% of the subjects evaluated
Eyelid edema	Dependent Qualitative ordinal	Absent Present	Must be recorded as absent in 95% of the subjects evaluated
Corneal epithelial defects	Dependent Qualitative ordinal	Affected area, percentage	Percentage of affected area less than 95%

The microbiological remission will be evaluated by means of the culture taken from the conjunctival sac fundus.

Variable	Operationalization	Measurement scale	Value
Culture	Dependent Discrete quantitative	UFC * / ml Eradication Reduction Proliferation	Must be recorded as absent in 95% of the subjects evaluated

* Colony forming units

The drugs under study will be considered effective if the patient has any of the following:

1. Clinical remission + Microbiological remission.
2. Clinical referral.
3. Microbiological remission.

Security measurements:

Adverse events and visual capacity.

Evaluation parameters

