- Any complication or lack of control that the doctor considers should be treated differently.

- **Elimination Criteria**

- Clinicians:

a. Any complication or lack of control that the doctor considers should be treated differently. The following points should be considered:

i. The no improvement of the initial clinical signs and symptoms.

ii. Diagnosis added or different to that of acute bacterial conjunctivitis.

iii. Use other medications outside the study.

b. * It is reiterated that they are minimum parameters to be considered, any other case in which the investigator considers necessary the elimination of the patient and suspension of the treatment must be informed and evaluated by the sponsor.

- For the sponsor:

- a. By its will, it will not have penalties, nor will it lose benefits to those that it already has right.
- b. For the total term of the scheduled visits in the clinical study.
- c. For a serious adverse event related to the medication that endangers your health.
- d. Why the medication does not work at the doctor's discretion.

and. Why, by sponsor's decision, the study ends earlier.

In case of withdrawal for any of these reasons or any other at the discretion of your doctor, you will be prescribed again the medication of which you were already a user or any other that is of benefit for your best treatment.

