15.3 Criteria for the premature withdrawal of the subject

Criteria for premature withdrawal

The following criteria will cause a mandatory withdrawal from the study:

The reasons for a patient leaving the study prematurely may be the following:

- Subject's decision. The patient who wishes to leave the study for any reason can do so at any time, but must inform the researcher. In all cases, the investigator should attempt to establish contact with the patient as soon as possible for a final evaluation in order to:
 - Document the patient's decision in clinical notes,
 - Obtain the reason (s) for the exit and write them down in the FRC exit format,
 - Evaluate the patient's clinical status,
 - If necessary, take the appropriate therapeutic measures: management of an adverse event.

In case of failure of all these attempts to contact the patient, the investigator may declare "loss of follow-up" of the patient. The investigator will document all the attempts in the corresponding medical file.

- Decision of the investigator. Especially if an adverse event occurs and the researcher considers that this may threaten the patient's health, or if an important disease occurs that requires the prescription of a medication incompatible with the objective of the study.
- Need for another treatment according to the criteria of the Medical Investigator who will have to document it well in his notes.
- Pregnancy (see procedure in Appendix 2)
- Any deviation to the protocol that affects the patient's safety.
- In all cases, the available data will be saved for the safety analysis (population evaluable by intention to treat).

Process

Whatever the reason for the premature discontinuation of the study treatment, the investigator should immediately inform Laboratorios Sophia S.A. of C.V. and the patient must return the rest of the study treatments to the center.

In case of premature withdrawal of treatment, the investigator should record the reason (s), the exact date of the premature discontinuation of the treatment in the source document and in FRC. If more than one reason is given, the investigator must indicate the main reason.

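### No culture or corneal staining is scheduled at the discontinuation visit, so patients withdrawn for non-improvement leave without a final microbiological result

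*Combined protocol and SAP*

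**What the plan says.** - **Efficacy.** Section 7.1 opens the main criterion with culture: "Efficacy will be determined by taking cultures of the lower conjunctival cul-de-sac", comparing baseline with final. It then adds reduction or absence of signs and symptoms as an and/or route. A drug counts as effective on clinical remission, microbiological remission, or both.
- **Schedule.** Table 2 has one column for unscheduled and discontinuation visits together, headed "Visita no programada / Descontinuación". It is not marked for "Toma de muestra para cultivo", for "Tinciones de fluoresceína/verde de lisamina" or for the clinical photograph. It is marked for symptoms, visual acuity, anterior and posterior examination, adverse events and concomitant drugs.
- **Exit.** The elimination criteria under Section 15.2 include "The no improvement of the initial clinical signs and symptoms". Section 15.3 adds "Need for another treatment according to the criteria of the Medical Investigator". On leaving, Section 15.3 asks for the decision, the reasons, the clinical status and any therapeutic measures. It names no swab and no stain.
- **Analysis.** Section 23 describes the variables in the intention-to-treat (ITT) set and runs the bivariate analysis in the per-protocol (PP) set. No rule for a missing final culture was found.

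**The concern.** Leaving early is tied to outcome. A patient who is not improving, or who needs something else, can be removed before day 8, and day 8 is the only post-baseline culture. There is no day 3 swab to fall back on. Section 15.2 says that withdrawn patients are prescribed their earlier medication or another one, so a swab taken some days later may reflect that treatment.

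Two results are lost. One is the microbiological component, which supplies every rate in the sample size calculation. The other is the composite status of a patient who has not remitted clinically: that patient is effective or not depending on a culture that was never taken.

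The working hypothesis in Section 6.1 is non-inferiority. If a weaker posology loses more of its non-responders, and only cultured eyes are compared, the arms look more alike than they are.

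**Working it through.** **1. What the sample size rests on.** Section 23 averages published rates of post-treatment culture eradication: 69.8% against 53.3% (absolute) and 92.34% against 66.12% (specific). With two-sided alpha 0.05, 80% power and a 1:1 ratio, Annex 1 gives m' = 135.272 and 36.373 before continuity correction. The correction is m = 0.25 m' × {1 + √[1 + 4/(m' × |P2 − P1|)]}².
- Absolute: 4/(135.272 × 0.165) = 0.179, so m = 147.1 (plan: 147; an independent run that rounds up gives 148).
- Specific: 4/(36.373 × 0.2622) = 0.419, so m = 43.7 (plan: 44).

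The plan's figures reproduce. They do not depend on the visit schedule, but they show that sizing uses the culture and not the clinical route.

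**2. What is recorded, from Table 2.**

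| Procedure | Day 1 | Day 3 | Day 8 | Discontinuation |
|---|---|---|---|---|
| Culture | X | – | X | – |
| Fluorescein/lissamine staining | X | X | X | – |
| Photograph | X | X | X | – |
| Ocular symptoms | X | X | X | X |
| Anterior biomicroscopy (includes epitheliopathy) | X | X | X | X |

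The visit lists in Section 18.2 place culture at the baseline and final visits and add none at early exit.

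**3. One arm, cultured eyes only.** The documents give no exit rate, so exit shares d of 5% to 20% are assumed. With true eradication p = 69.8% and eradication q among exits, the observed rate is (p − d·q)/(1 − d).
- q = 0: d = 5% gives 0.698/0.95 = 73.5%; 10% gives 77.6%; 15% gives 82.1%; 20% gives 87.2%. At 60 eyes per arm these are 3, 6, 9 and 12 eyes without a final culture.
- q = 53.3% (the plan's placebo rate): 70.7% at d = 5%, rising to 73.9% at d = 20%. The inflation is then small.

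**4. Two arms, 60 eyes each, all exits being failures, cultured eyes only.**
- True 55% (33/60) against 70% (42/60). Exits of 20% and 5% leave 48 and 57 eyes: 33/48 = 68.8% against 42/57 = 73.7%. A true 15-point deficit appears as 4.9 points.
- Equal exits of 10% leave 54 eyes each: 33/54 = 61.1% against 42/54 = 77.8%. The gap is 16.7 points, so it does not shrink.
- True 59.8% against 69.8% (−10.0 points): exits of 15% and 5% give −3.1; 20% and 5% give +1.3; equal 10% gives −11.1.

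**5. Counting every exit as a failure, with no new swab.** If all exits are failures, 33/60 and 42/60 return and the 15-point gap is restored. If 53.3% of exits were in fact eradicated, a true 69.8% is reported as 67.1% (d = 5%) down to 59.1% (d = 20%). Without exit cultures nobody can tell which case applies.

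**The case against.** The strongest objection is that culture is only one of two routes to efficacy. Section 7.1 accepts clinical remission alone, and the discontinuation column marks "Sintomatología Ocular (A,B,C,D" and "Biomicroscopia anterior (F,G,H,I,J,K", which cover secretion, hyperemia, chemosis, eyelid edema and epitheliopathy. This stands. A reader might infer that the main endpoint as a whole is missing for patients who leave; the documents do not support that. What is missing is the microbiological component and, for clinical non-improvers, the composite that depends on it.

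A reader might also infer that there is no corneal result at exit. Epitheliopathy is still recorded. What is unscheduled is the stain grade, the likely source for the percentage of affected area in Section 7.1.

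Nor can eliminated patients be equated with treatment failures. Non-improvement is listed as a point to consider, beside a different diagnosis and use of other medication, and a non-improver with microbiological remission counts as effective under the plan's own rule. The last point also works against the schedule, because that status cannot be settled without the swab.

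Finally, the bias in the illustration comes from analysing cultured eyes only, a rule that the plan does not state, and step 5 shows that a failure rule alone can restore the gap. This is right as far as it goes. The schedule and the missing-data rule must be fixed together: an exit swab that never leaves a PP-only comparison achieves little, and an on-treatment negative swab could turn a clinical failure into a success.

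**Conclusion.** The point holds in limited form. As scheduled, patients who leave for non-improvement or another treatment have clinical signs but no final culture and no stain grade. The endpoint used for sizing is therefore missing in a group selected by outcome, and a swab that was not taken cannot be recovered by analysis.

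The documents do not show that a biased comparison will follow. The shift from 15 to 4.9 points rests on three assumptions: exits of 20% against 5%, no eradication among exits, and analysis of cultured eyes only. With equal exits the gap does not narrow, and with 53.3% eradication among exits the single-arm inflation is 0.9 to 4.1 points (70.7 − 69.8 and 73.9 − 69.8). The plan gives no elimination rate and no non-inferiority margin, so the practical effect cannot be fixed more closely. This is a cheap improvement worth making before enrolment.

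**What to change.** **Schedule.** Split the shared column of Table 2 into unscheduled and discontinuation visits. Mark culture and staining for discontinuation only, replacing the day 8 sample. Mark the photograph too; Section 8 already requires one at each visit. In Section 15.3, name the exit swab as the end culture and record the study day, whether the patient was still on study drug, and whether another antibiotic had already been started. Treatment should not wait on the sample.

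**Analysis.** In Section 23, run the comparison on the ITT set as well as PP. In the main ITT analysis, count patients withdrawn for non-improvement or need for other treatment as failures. Use the exit culture for the microbiological component and in a sensitivity analysis. State how any final culture that is still missing is counted.

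**Cost.** A table edit and a few sentences. With the column split, the day 8 swab and stain are moved forward and not added. If the shared column were marked as it stands, patients with an unscheduled visit who also reach day 8 would be sampled an extra time. The downside is that exit cultures fall on varying days and may show on-treatment suppression.
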